5.2.2.2 All Other Days

Patients will be instructed to have the following tests done at their local clinical laboratory at the frequency listed below:

- CBC with Differential, ANC, platelet count weekly i.e., Day 8, 15 and 22nd of Cycle 2 and 3.
- Blood Chemistry Chem-20 test Panel, every two weeks i.e., Day 15 of Cycles 2 and 3.
- The Investigator and/or research staff will immediately contact the patient to notify him/her to interrupt study medication if the laboratory test results meet the interruption criteria. The Investigator will continue to review the laboratory test results and inform the patients about how to proceed regarding study medication (i.e., re-starting or continue to hold).
- Patients will continue to self-administer study medication per instructions twice daily at approximately 12 hour intervals in an out-patient setting.

5.2.3 Each Subsequent Visit – Day 1

- All study visit specific observations as outlined in "Study calendar" and described for Day 1 of Cycle 2 and 3 will be done for each subsequent visit on Day 1.
- In addition, Day 1 of Cycle 4 the following procedures will be done:
 - Bone marrow aspiration or biopsy and cytogenetics (if abnormal prior to therapy) will be done (Cycle 4, Cycle 7 and each sixth subsequent cycle)
 - o Plasma and whole blood PD biomarkers sample collection pre-dose
 - Cytogenetics may be performed on peripheral blood (if bone marrow aspiration is inadequate)
- A 3-month supply of study medication will be dispensed on Day 1 of each subsequent visit to qualified patients who have not met any interruption criteria and showing clinical benefit from the therapy.
- Patients will be instructed to return to the site every three months (+/- 7 days) following Day 1 of Cycle 4 and bring their study medication including empty containers with them.
- Patients will be instructed to go every two weeks for the next three months to their local laboratory to have blood drawn for CBC with Differential, ANC and platelet count.
- Due to PD samples being collected at the next visit, patients will be asked to withhold their morning dose of study medication on Day 1 of each subsequent visit.

 Patients will be instructed to call the Investigator or designated research staff if they experience any "troubling" signs and/or symptoms that are of moderate or greater severity.

5.2.4 Each Subsequent Visit - All Other Days

- Review all safety information and criteria for dosing interruptions on a regular and on-going basis to determine if patients should receive further doses.
- The Investigator and/or research staff will immediately contact the patient to notify him/her to interrupt study medication if the laboratory test results meet any interruption criteria. The Investigator will continue to review the laboratory test results and inform the patients about how to proceed regarding study medication (i.e., re-starting or continue to hold).
- The investigator and/or research staff will contact the patient on a regular monthly basis to assess the patient's overall well-being, any new or worsening signs and/or symptoms, compliance with study medication and dosing instructions, compliance with the local laboratory schedule and to answer any questions that the patient might have. The investigator and/or research staff will remind the patient of their next scheduled visit and how to prepare for it (i.e., withhold their morning dose of study medication.) The investigator and research staff will be responsible for ensuring that all relevant information resulting from these monthly contacts is documented in the patient's medical record and case report form, as appropriate.

5.2.5 End of Study or Early Termination Visit

- All study visit specific observations as outlined in "Study calendar" and described above for Day 1 of Cycles 2 and 3 will be done except:
 - Study medication will not be dispensed.
 - Blood draw for PK sampling will not be done.

5.2.6 Duration of Participation and Number of Subjects

The individual patient participation is expected to be 4-12 months. A maximum total number of 30 patients can be recruited into each disease category arm of this study and therefore the maximum total number of patients potentially studied under this protocol would be 120.

6. RESPONSE DEFINITIONS

Patients will be assessed for efficacy at the end of each 28 day cycle of therapy, +/-4 days for the first 3 cycles, then 3 monthly thereafter.

6.1 Acute leukemias, MDS, CML-BP, CMML:

- 6.1.1 Complete remission: The patient must be free of all symptoms related to leukemia and have an absolute neutrophil count $\geq 1 \times 10^9 / L$ and platelet count $\geq 100 \times 10^9 / L$, and normal marrow differential ($\leq 5\%$ blasts) in a normo- or hypercellular marrow.
- 6.1.2 Partial remission: CR with 6-25% abnormal cells in the marrow or 50% decrease in bone marrow blasts.
- 6.1.3 CRp: As per CR but platelet count <100 x109/L.
- 6.1.4 Hematologic Improvement (HI)

Hematologic improvement should be described by the number of individual, positively affected cell lines (e.g. HI-E; HI-E + HI-N; HI-E+ HI-P + HI-N).

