3.1 Inclusion Criteria

- A. Must be at least 18 years of age.
- B. Patients must have relapsed/refractory leukemias for which no standard therapies exist. Patients with poor-risk myelodysplasia (MDS) [i.e. refractory anemia with excess blasts (RAEB-1 or RAEB-2) by WHO classification] and chronic myelomonocytic leukemia (CMML) who failed prior therapy are also candidates for this protocol. Relapsed/refractory leukemias include acute non-lymphocytic leukemia (AML) by WHO classification (i.e. ≥ 20% blasts), acute lymphocytic leukemia (ALL), or chronic myelogenous leukemia (CML) in blast crisis. Patients with CML who are resistant to at least two tyrosine kinase inhibitors and have no standard stem cell transplant option are also eligible.
- C. ECOG performance status of 0-2.
- D. A female of childbearing potential must have a negative serum or urine pregnancy test at screening. Women of child-bearing potential (i.e., women who are premenopausal or not surgically sterile) must use acceptable contraceptive methods (abstinence, intrauterine device [IUD], oral contraceptive or double barrier device), and must have a negative serum or urine pregnancy test within 2 weeks prior to beginning treatment on this trial. Sexually active men must also use acceptable contraceptive methods for the duration of time on study.

- E. Must be able and willing to give written informed consent.
- F. In the absence of rapidly progressing disease, the interval from prior treatment to time of study drug administration should be at least 2 weeks for cytotoxic agents, or at least one week for noncytotoxic agents. Persistent clinically significant toxicities from prior chemotherapy must not be greater than grade 2.
- G. Patients must have the following clinical laboratory values unless considered due to leukemic organ involvement:
 - 1. Serum creatinine ≤ 2.0 mg/dl.
 - 2. Total bilirubin ≤ 1.5x the upper limit of normal unless considered due to Gilbert's syndrome or hemolysis.
 - 3. Alanine aminotransferase (ALT), and aspartate aminotransferase (AST) \leq 2.5x the upper limit of normal unless considered due to organ leukemic involvement (then \leq 5x the upper limit of normal).
 - H. Patients with active CNS disease are included and will be treated concurrently with intrathecal therapy. INCB018424 will not be administered by intrathecal route.

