4.2 Administration of INCB018424

This is an open label, non-randomized, study of INCB018424, administered orally to patients with relapsed/refractory AML, ALL, and MDS (including CMML), and blast phase or tyrosine kinase refractory CML. The study of INCB018424 in each disease listed will be conducted in two parts. The first part is intended to enroll a maximum of 10 patients within each of the four disease categories included in this study and to identify whether significant benefit is observed. If a minimum of one patient shows benefit that is considered significant, there will be an expanded cohort of 20 additional patients treated in that arm of the study.

Patients will receive 50 mg/day administered orally in two divided doses (i.e., BID: every 12 hours \pm 2 hours). Within each arm of the study, three patients will be initially treated and observed for toxicity for one treatment cycle (28 days) before the additional seven patients are entered. Dose reduction will be considered if the number of patients experiencing grade 3 or higher toxicities exceed 2/3, 3/4, 4/7, 5/10, 6/14, 7/18, 8/22, 9/26. Treatment will be administered primarily on an outpatient basis, but can be administered as an inpatient if the patient is hospitalized for other reasons.

The 5 mg tablets have been shown to be stable when stored up to one month at 25° C/60%RH and 40° C/75%RH; the 25 mg tablets have been shown to be stable when stored for three months at 25° /60%RH and 40° /75%RH. (25° C = 77° F, 40° C = 104° F).

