5.2 Study Procedures

•	Screening Phase	Treatment Phase								End of Treatment		
Visit	Day -28 to Day -1	Cycle 1			Cycle 2+3			Subsequent Visits - For details see Footnotes		1		
		Day 1	Day 8	Day 15	Day 22	Day 1	Day 8	Day 15	Day 22	Day 1	Day 15	End of Study ^o
Evaluation – All evaluations have a												•
+/- 2 day window except for bone												
marrow biopsy (see footnote i).												
Informed consent ^a / Eligibility criteria	X	X										
Medical & medication history ^b	X	X	X	X	X	X				X ^b		X
Physical examination ^c	X	X	X	X	X	X				X ^c		X
Vital signs ^c	X	X	X	X	X	X				X ^c		X
Overall Response assessment (IWG-MRT) ^d						X				X ^d		X
ECOG performance status ^e	X					X				Xe		X
Concomitant medication review ^f		X	X	X	X	X				X ^f		X
Clinical laboratory tests ^g	X		X	X	X	X		X		X ^g		X
CBC ^h	X		X	X	X	X	X	X	X	X ^h	X^h	X
PT/PTT	X											
CXR	X											
Pregnancy test ^g	X											
FSH test ^g	X											
Serology / HIV laboratory tests ^g	X											
Urinalysis ^g	X											
BM aspiration, biopsy and cytogenetics ⁱ	X									Xi		
Administer 1st dose of INCB018424 ^j		X										
Dispense INCB018424 study medication ^j		X				X				X ^j		
PK sampling ^k		X				X						
PD biomarker sampling ¹		X				X				X ¹		X
Adverse event / Intercurrent illness assessment ^m		X	X	X	X	X				X ^m		X
Study medication compliance ⁿ			X	X	X	X				X ⁿ		X

- a. Informed consent must be obtained at Screening. At Screening and Day 1, assess eligibility for study entry and review eligibility for study entry on Day 1.
- b. Medical history will be done at each visit. Medication history will be obtained only at the screening visit.
- c. A complete examination will be performed at Screening and the End-of-Study Visit . A "targeted" examination will be performed at all other visits. During the treatment phase, weekly visits at the local physician's office are required during 1st cycle of therapy with a review of constitutional symptoms and physical exam, including transfusion requirement. During 2nd and 3rd cycles visits are every 4 weeks, and then every 3 months thereafter. All examinations will include body weight. On Day 1 of Cycle 1, before PK/PD blood-draws, the vital signs will be done as well as with the physical exams. On all other clinical visits vital signs are taken once. Overall response assessments will be graded according to consensus criteria for treatment response.

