9.1.1 Selection of Sample Size

This phase II study will use a Gehen's design. Assuming a null response rate of 0%, targeting a 15% response rate and power=80%, the trial will initially enroll 10 patients in each disease category: 1) AML; 2) ALL; 3) MDS; and 4) CML. If at least one response is achieved in the 10 patients in a disease

Category, then a total of 30 patients will be enrolled in this disease category. Thirty patients will provide a confidence interval for response rate with half-width=0.13, assuming the true response rate is 15%. The total sample size is 120.

For toxicity evaluation, patients enrolled in the study will be considered in 2 cohorts (I) those with relapsed/refractory AML, ALL, and MDS (including CMML), and blast phase CML, and (II) those with chronic phase CML. At any time after 6 patients are enrolled in cohort I (including AML, ALL, MDS, blast phase CML patients), if 30% or more patients experience grade 3 or 4 toxicity thought to be directly related to INCB018424 and lasting longer than 2 weeks, then we will stop that cohort of the trial. At any time after 6 patients are enrolled in cohort II (including chronic phase CML patients), if 15% or more patients experience grade 3 or 4 toxicity thought to be directly related to INCB018424 and lasting longer than 2 weeks, then we will stop that cohort of the trial.

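### The response that decides expansion is not measured or defined consistently: no scheduled marrow by week 8 for non-escalated patients outside chronic phase CML, two different go rules, and a PR limb with no baseline comparison

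*Combined protocol and SAP*

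**What the plan says.** **Design.** Section 9.1.1 is a Gehan design: "Assuming a null response rate of 0%, targeting a 15% response rate and power=80"%. Ten patients enter each of four disease categories. The go rule begins "If at least one response is achieved in the 10 patients in a disease" category, and a pass takes that category to 30. Section 4.2 states the rule differently: "If a minimum of one patient shows benefit that is considered significant, there will be an expanded cohort of 20 additional patients".

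**Response definitions.** Section 6.1.1 requires for CR freedom from leukemia symptoms, ANC of at least 1 and platelets of at least 100 (×10⁹/L), and at most 5% blasts in a normo- or hypercellular marrow. Section 6.1.2 then gives "Partial remission: CR with 6-25% abnormal cells in the marrow or 50% decrease in bone marrow blasts". CRp and hematologic improvement (HI) are defined separately in 6.1.3 and 6.1.4, and CML has its own criteria in 6.2. The assignment list in 9.5.2 includes complete and partial response but neither CRp nor HI. The study calendar in 5.2 labels its response row "Overall Response assessment (IWG-MRT", and footnote c says "Overall response assessments will be graded according to consensus criteria for treatment response".

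**Timing.** Section 4.1 places the response used for statistical evaluation after two cycles (8 weeks). For patients escalated to the higher dose it falls after two cycles at that dose, and chronic phase CML is assessed at 3 months. Section 4.4 lists lack of objective response after 2 cycles (3 if escalated after cycle 1) as a reason to end treatment, unless the drug is considered to be of clinical benefit. Footnote i of 5.2 and section 7.3 schedule marrows at screening, at the start of Cycle 4, at Cycle 7 and at every sixth cycle after that. The end-of-study column and section 5.2.5 have none.

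**Entry.** Section 3.1 B admits "acute non-lymphocytic leukemia (AML) by WHO classification (i.e. ≥ 20% blasts") and MDS that is "refractory anemia with excess blasts (RAEB-1 or RAEB-2) by WHO classification".

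**The concern.** One event among 10 patients decides whether 20 more are enrolled, so the rule is only as good as the scoring of that event. Three things weaken it.

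- The measurement that CR and PR depend on is not scheduled at the time the response is taken for a large class of patients.
- Two sections name different qualifying events.
- One limb of PR can be met by a patient who has not changed.

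The first can close an arm in which the drug works. The second can go either way. The third can open an arm in which it does not. What is at stake is the correctness of each expansion decision and the meaning of the stated 80% power.

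**Working it through.** **The plan's own figures (inputs from 9.1.1).** The chance of passing the gate is 1 − (1 − p)^10.

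- At p = 0.15: 1 − 0.85^10 = 0.803. With 9 patients, 1 − 0.85^9 = 0.768, so 10 is the smallest number that reaches 80%.
- At p = 0: 0, so there is no false expansion.
- Half-width at 30 patients: 1.96 × √(0.15 × 0.85 / 30) = 0.128, stated as 0.13.

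The sample size is correctly calculated.

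**(a) Assessment against marrow (28-day cycles, days from start).**

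| Patients | Statistical response (4.1) | First repeat marrow (5.2 footnote i, 7.3) |
|---|---|---|
| Not escalated, not chronic phase CML | 2 × 28 = day 56 | 3 × 28 = day 84, ±7 |
| Escalated after cycle 1 | (1 + 2) × 28 = day 84 | day 84, ±7 |
| Chronic phase CML | 3 months | day 84, ±7 |

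Only the first row conflicts. The windows do not close the gap. With the ±4 days of section 6, the latest assessment is day 56 + 4 = 60 and the earliest marrow is day 84 − 7 = 77, which leaves 17 days.

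CR, CRp and PR all rest on a marrow finding. Of the categories in 6.1, only HI can be scored from scheduled tests at week 8. A patient who stops at that point under 4.4 has no scheduled post-baseline marrow at all. If only a share s of true responders is recognised, power is 1 − (1 − 0.15s)^10, which is below 0.803 for any s below 1. The documents give no value for s.

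**(b) The two go rules.** Both need one patient in 10 and both add 20, but on different events.

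- A patient with HI only could be judged to have significant benefit under 4.2. If the list in 9.5.2 defines response, 9.1.1 is not met.
- A patient with PR that is not judged significant meets 9.1.1 on that same list but not 4.2.

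The conflict therefore has no fixed direction.

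**(c) The 6-25% limb.** Only the second limb of PR refers to change. The conditions carried over from CR are also absolute levels. AML may enter from 20% blasts, so 20-25% lies inside the band. MDS with excess blasts lies below the AML threshold and can lie inside it too. The laboratory criteria in 3.1 G cover creatinine, bilirubin and transaminases, with no minimum for ANC or platelets. No section says that criteria already met at entry are not a response.

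The no-effect rate p at which the false expansion probability reaches t is p = 1 − (1 − t)^(1/10):

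- t = 0.05: p = 0.0051
- t = 0.10: p = 0.0105

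These values show how little tolerance a 1-in-10 gate has. They do not estimate how often 6.1.2 would misfire.

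**The case against.** The strongest reply concerns (c). To score PR without change, a patient with relapsed or refractory disease, or failed prior therapy, must already be symptom-free with adequate counts and a normo- or hypercellular marrow. That is probably rare. Sections 4.1 and 9.5.2 also separate stable disease from response, which is the natural place for an unchanged patient. And (a) largely blocks this route at week 8, because without a marrow the 6-25% limb cannot be scored then. All of this stands and limits the weight of (c). It does not remove the point: section 6 does not define stable disease, and moving the assessment to a scheduled marrow would reopen the route unless 6.1.2 is also corrected.

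On (b), it is fair to say that 9.5.2 invites reading response as CR or PR. But 9.1.1 does not refer to it, and 6.1.4 itself calls HI grades responses. The calendar's IWG-MRT label is mostly editorial, since section 6 sets out its own criteria in full.

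On (a), an unscheduled marrow at week 8 is not prohibited, and 4.4 lets patients with clinical benefit continue. Both soften the problem. Neither makes the measurement part of the plan.

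A reader might infer that the sample size is wrong, or that inactive arms will often expand. The documents support neither. The figures in 9.1.1 reproduce, no no-effect rate is given, and the rate may be near zero. Section 9.2.1 calls the efficacy analyses exploratory, so no error-controlled test is compromised.

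**Conclusion.** The point holds and should be fixed. The response behind the expansion rule is not measured or defined consistently.

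- **(a)** is the firmest part. It follows from the schedule alone, applies to non-escalated patients outside chronic phase CML, and tends towards missed responses. The stated 80% power presumes a measurement that the calendar does not supply at week 8. The size of the loss cannot be derived.
- **(b)** affects all four categories, and its direction is unknown.
- **(c)** means that the 0% null is not strictly assured. It is probably a rare event. The only number attached is the gate's tolerance: more than 5% false expansion once the no-effect rate exceeds about 0.5%.

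The 10 patients, 80% power and 0.13 half-width stand as calculated. The conclusion assumes 28-day cycles without delay and that CR and PR count towards the gate, which 9.1.1 does not say.

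**What to change.** 1. Reconcile 4.1 and 4.4 with footnote i of 5.2 and with 7.3, so that the statistical response rests on a post-baseline marrow that is already scheduled. Do this by aligning dates, not by adding a procedure. How 4.4 is reconciled is for the sponsor to decide.
2. Put one identical go rule in 4.2 and 9.1.1 that lists the qualifying categories. Include those of 6.2 that count for CML, and say whether CRp and HI count.
3. In 6.1.2, require for the 6-25% limb a decrease in marrow blasts from baseline, of a size fixed in advance. State that criteria already met at baseline are not a response.
4. State that section 6 governs over the calendar's IWG-MRT label and footnote c, or name the set that does.

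The cost is mainly wording. An assessment or marrow date may move, and slightly fewer patients may count as responders. The sponsor should confirm that the 0% null and 15% target apply to the category list it adopts.

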9.5 Reporting and Exclusions

9.5.1 Evaluation of toxicity.

All patients will be evaluable for toxicity from the time of their first treatment with INCB018424.

9.5.2 Evaluation of response.

All patients included in the study must be assessed for response to treatment, unless there are major protocol treatment deviations or they are ineligible. Each patient will be assigned one of the following categories: 1) complete response, 2) partial response, 3) stable disease, 4) progressive disease, 5) early death from malignant disease, 6) early death from toxicity, 7) early death because of other

cause, or 8) unknown (not assessable, insufficient data). [Note: By arbitrary convention, category 9 usually designates the "unknown" status of any type of data in a clinical database.]

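### Partial remission in 6.1.2 can be read as a bare 50% fall in marrow blasts with no baseline floor, so in MDS/CMML counting error alone could open the 1-in-10 expansion gate

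*Combined protocol and SAP*

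**What the plan says.** Section 6.1 gives one set of response definitions for acute leukemias, MDS, blast-phase CML and CMML. Complete remission (6.1.1) opens with "The patient must be free of all symptoms related to leukemia and have an absolute neutrophil count", then adds a platelet requirement and a marrow with at most 5% blasts. Partial remission (6.1.2) is "CR with 6-25% abnormal cells in the marrow or 50% decrease in bone marrow blasts". No baseline blast level, absolute fall, number of cells counted or confirmatory marrow is attached to the second limb. Section 7.3.1 leaves the marrow reading to the hematopathologist's usual method.

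Section 3.1 B limits MDS to RAEB-1 and RAEB-2, without giving blast percentages for those classes. It then says that patients with "chronic myelomonocytic leukemia (CMML) who failed prior therapy are also candidates for this protocol", with no blast requirement. The objectives place CMML within MDS.

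The design in Section 9.1.1 rests on "Assuming a null response rate of 0%, targeting a 15% response rate and power=80"%. The gate reads "If at least one response is achieved in the 10 patients in a disease" category, after which enrolment goes to 30. Section 4.2 words the same gate differently: "If a minimum of one patient shows benefit that is considered significant". Section 9.5.2 keeps partial response apart from stable disease: "Each patient will be assigned one of the following categories: 1) complete response, 2) partial response, 3) stable disease".

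**The concern.** A relative fall with no floor is fragile when the starting count is small. If the second limb stands alone, a CMML patient read at 3% blasts before treatment and 1% afterwards is a partial remission, although both readings already lie within the 5% marrow limit for CR. On a differential of a few hundred cells, such a change can be counting error.

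The gate has no tolerance for this. With a null rate of exactly 0%, one response is taken as proof of activity. If unchanged patients can be scored as responders, an inactive drug can earn 20 more patients in the MDS category, and the same false responses enter the final rate.

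The protocol guards against this elsewhere. The minor platelet response in 6.1.4.2 pairs its 50% rise with a baseline limit and a minimum net increase, and CML hematologic response in 6.2.1 has a confirmed form, met again at least 28 days later. The marrow-blast limb has neither safeguard.

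**Working it through.** **The plan's own figures.** The chance of at least one response in 10 at a true rate of 15% is 1 − 0.85^10 = 0.803, against the stated 80%. The half-width at 30 patients is 1.96 × √(0.15 × 0.85 / 30) = 0.128, against the stated 0.13. Both reproduce. At a true 0% rate the gate opens with probability 0.

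**Inputs that the documents do not give (assumptions).** Differential of 200 or 500 cells. True blasts, unchanged by treatment: CMML 3%, RAEB-1 7%, RAEB-2 12%. Ten patients: 3 CMML, 3 RAEB-1, 4 RAEB-2. One repeat marrow in all ten. Binomial counting error only. The 50% limb stands alone.

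**Per-patient false halving.** With independent counts X1 and X2 ~ Binomial(N, p), q = P(X2 ≤ X1/2).

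| True blasts | 200 cells | 500 cells |
|---|---|---|
| 3% | 0.1522 | 0.0395 |
| 7% | 0.0423 | 0.00245 |
| 12% | 0.0089 | 0.00007 |
| 20% (AML entry level) | 0.0006 | below 0.00001 |

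**False opening of the gate**, 1 − Π(1 − q):
- Mixed group, 200 cells: 1 − 0.8478³ × 0.9577³ × 0.9911⁴ = 1 − 0.609 × 0.878 × 0.965 = 0.48.
- Mixed group, 500 cells: 1 − 0.886 × 0.993 × 0.9997 = 0.12.
- Without CMML (5 RAEB-1, 5 RAEB-2): 1 − 0.9577⁵ × 0.9911⁵ = 0.23 at 200 cells; 0.013 at 500.
- Mixed group with repeat marrows in half the patients (each q halved): 0.27 or 0.06.

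**Effect on the final rate.** The mean false-response rate in the mixed group is (3 × 15.2 + 3 × 4.2 + 4 × 0.9)/10 = 6.2 percentage points at 200 cells and 1.3 points at 500. The planned half-width is 13 points.

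**Effect of a fix**, applied to the observed baseline:

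| Rule, mixed group | 200 cells | 500 cells |
|---|---|---|
| As worded, limb standing alone | 0.48 | 0.12 |
| Baseline above 5% | 0.20 | 0.014 |
| Baseline above 5% and fall of at least 5 points | 0.11 | 0.003 |

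The floor works by lowering q at 3% blasts from 0.152 to 0.021 (200 cells). At 7% it barely moves q (0.0423 to 0.0419); there the absolute fall does the work (0.0253). Without CMML, both conditions together lower the chance only from 0.23 to 0.16 (200 cells) or from 0.013 to 0.005 (500 cells).

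**The case against.** The strongest objection is grammatical. The opening words of 6.1.2 can govern both limbs, so that blood-count and symptom conditions for CR are needed as well. A reader might infer that the problem survives this reading, because some patients enter with preserved counts and no symptoms. The documents do not support that inference. On this reading an unchanged patient with such counts and 6–25% blasts is already a partial remission by the first limb. One at 5% or below already meets CR, or CRp if only platelets are low, taking the blast limit as the marrow test. The second limb then adds very little in MDS/CMML, and the fault would lie in the other criteria. This objection stands, and it makes the figures above conditional on the free-standing reading.

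Other points also stand in part:
- Cell count, case mix and blast levels are all assumed. CMML drives the result, and without it 500 cells give only 1.3%.
- Not all ten patients need have a repeat marrow. The first is scheduled at Cycle 4 (Sections 5.2 and 7.3), while Section 4.1 places the statistical response assessment after two cycles and Section 4.4 allows treatment to end then for lack of response. These passages need reconciling.
- Section 4.2 asks for benefit judged significant, which leaves room not to count a 3%-to-1% change. It gives no criterion, however, and 9.1.1 asks only for a response.
- Section 9.2.1 calls the efficacy analyses exploratory.

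Against this, sampling variation between aspirates, which is left out here, would raise every figure.

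**Conclusion.** The concern holds in a conditional form. Section 6.1.2 admits a reading under which a halving of marrow blasts, from any starting level, is a response. On that reading the 0% null behind the MDS gate is not safe: the chance of a false opening is about 48% (200 cells) or 12% (500 cells) for the assumed mix, 23% or 1.3% without CMML, and 27% or 6% if half of the mixed group have a repeat marrow. The problem is concentrated at low baseline counts and is negligible at 20% blasts.

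A reader might go further and infer that an inactive drug will probably expand, or that the final MDS rate is seriously biased. The documents do not support that. They fix neither the cell count nor the case mix, they leave the syntax open, and the computed bias of 1.3 to 6.2 points is smaller than the planned half-width. This is a definition that should be fixed before the gate is applied; it is not a flaw that invalidates the design.

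**What to change.** Amend 6.1.2 as follows, and use the same definition for the 1-in-10 gate and for the final response rate:
1. State whether the CR conditions apply to both limbs or only to the first.
2. Let the 50% limb count only when baseline marrow blasts exceed 5%, preferably with a minimum absolute fall as well. Five percentage points is an example; the value is assumed and has no source in the documents.
3. State that a patient at or below 5% blasts at baseline cannot be scored a responder on the marrow criterion without change from baseline. Without this sentence, a CMML patient excluded from the 50% limb could still be scored as CR with no change.

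These conditions reduce the risk without removing it. A stated minimum number of cells for the differential would help further, since the residual risk is much larger at 200 cells than at 500.

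The cost is a few sentences, using marrow data already collected. The downside is a slightly lower MDS/CMML response rate. The change should be made before any borderline response is seen, because a redefinition afterwards would be post hoc.
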